14.2.2 Primary Endpoint Analysis

The primary end-point of this phase II study is the correlation biomarkers with overall response in AML/MDS patients to decitabine.

We will correlate the presence of patient specific mutations (especially mutations in *DNMT3A*, *IDH1*, *IDH2*, and *TET2*) with overall response rates. Mutation rates in these genes and in other patient-specific genes will be correlated with overall response and their respective 95% confidence intervals will be provided.

Statistical considerations. The relationship between AML/MDS-associated mutations and the responsiveness to decitabine will be described by contingency tables and assessed using Chi-square test or Fisher's exact test as appropriate. The differentially expressed genes between responders and non-responders will be determined using the significance analysis of microarray (SAM). Multivariate logistic regression will also be fit to adjust the potential confounding effects of other demographic and clinical characteristics. The resultant critical *P* values will be corrected for multiple testing. Since the Bonferroni correction is known to be too conservative, a permutation analysis (e.g., 10,000 random assignments for

responsive status) will be used to derive an empirical critical P value. The new critical p-value is the number of permutation tests which yield a lower p-value than the original test divided by the total number of permutation tests.[61]

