A power analysis was performed using Chi-square test for the association between mutation and response to decitabine. The frequency of *DNMT3A*, *IDH1/2*, and *TET2* mutations in AML and MDS patients are each between 15% and 30% in multiple cohorts.[29-37] **Table 3** shows the minimal detectable differences of response rates between mutant and wild-type cases, assuming an expected overall 45% CR/CRi rate and 80% power. For an average of 20% frequency of a mutated gene, for example, 100 patients will provide 80% power to detect 30% difference at a 2-sided 0.1 alpha error. The purpose of this study is to determine whether any of these mutations result in a clinically significant association that would warrant pre-treatment testing. We believe that a reasonable cut off would be if at least 30% of clinical response could be attributed to the presence of a specific mutation. However, we anticipate that more power could be achieved as we assess patient groups with combined characteristics (e.g. *DNMT3A* mutation or loss of *DNMT3A* expression). In addition, we expect that the majority of the enrolled 125

Table 3. Detectable mutation associated response rates (80% power, $\alpha = 0.05$)

Total N	% of patients with a given mutation	Detectable response difference	Sensitivity of mutation to predict response at minimum detectable response difference*
100	15%	0.40	80%
	20%	0.35	75%
	30%	0.30	67%
	40%	0.27	61%
	50%	0.26	58%

* Assuming the overall response rate (CR/CRi) of 45%

patients can be used in the analysis (since all of our molecular information will be acquired within 30 days of enrollment, we anticipate a drop-out rate of 20% or less).

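### The primary mutation–response test is powered at two different alphas, and neither allows for the promised multiple-testing correction: over three or four gene tests, power for a 30-point difference is 46–62%, not 80%

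*Combined protocol and SAP*

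**What the plan says.** All of this is in Section 14.2.2, Primary Endpoint Analysis, and the text is the same in each protocol version in the file.

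- **Method:** "A power analysis was performed using Chi-square test for the association between mutation and response to decitabine". The inputs are then given as "assuming an expected overall 45% CR/CRi rate and 80% power".
- **Power sentence:** taking a gene that is mutated in one patient in five, the plan states that "100 patients will provide 80% power to detect 30% difference at a 2-sided 0.1 alpha error".
- **Table 3:** the caption gives 80% power at alpha 0.05, with N = 100. The detectable differences are 0.40, 0.35, 0.30, 0.27 and 0.26 for mutation frequencies of 15%, 20%, 30%, 40% and 50%.
- **Multiplicity:** the critical P "values will be corrected for multiple testing". Bonferroni is set aside as too conservative in favour of about 10,000 random reassignments of response status. The new value is the share of permutations whose p-value is lower than that of the test as observed.
- **What is tested:** DNMT3A, IDH1, IDH2 and TET2 are singled out, and other patient-specific genes are added without a count. The power paragraph treats IDH1/2 as one group.

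Neither Section 14.2.2 nor Section 14.3 says which alpha decides the primary analysis, whether it applies per gene or across genes, or how many tests form the family.

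**The concern.** For the same case (20% frequency, 100 patients) a reader finds two detectable differences at two significance levels and cannot tell which one the analysis will use. Both come from a single test at its nominal level, while the analysis is to test several genes and correct for it. A correction that works across genes tightens the threshold for each gene and lowers power. If it does not tighten the threshold, it is not controlling error across genes.

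This concerns the trial's only primary objective. If no gene reaches significance, that result will be read against the 80% in the protocol, so the figure should describe the test that is actually carried out.

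**Working it through.** **Inputs, all from Section 14.2.2.** N = 100; mutation frequency 20%, so 20 mutant and 80 wild-type patients; overall response 45%; difference d = 0.30 in the text and 0.35 in Table 3; chi-square test. Alpha is two-sided 0.10 in the text. Table 3's 0.05 is taken as two-sided.

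**Response rates consistent with 45% overall.** Mutant = 0.45 + 0.80 × 0.30 = 0.69; wild-type = 0.45 − 0.20 × 0.30 = 0.39.

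**Formula** (two proportions, pooled variance under the null): power = Φ[(d − z × SE0) / SE1].

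- SE0 = √[0.45 × 0.55 × (1/20 + 1/80)] = 0.1244
- SE1 = √[0.69 × 0.31/20 + 0.39 × 0.61/80] = 0.1169

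**The plan's own figures first.**

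- Text, alpha 0.10: (0.30 − 1.645 × 0.1244) / 0.1169 = 0.816, so power is 79.3%. The stated 80% reproduces.
- Table 3, 20% row, d = 0.35 (0.73 against 0.38), alpha 0.05: power is 82.6%. The difference giving exactly 80% is about 0.34. This row is slightly conservative.

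The two statements are therefore numerically compatible, each at its own alpha.

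**The 30-point difference at other levels.** The number of tests m is an assumption: 3 if IDH1/2 is one group, 4 if the genes are tested separately. The corrected threshold is approximated by alpha/m.

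| Family alpha | Tests | Per-test level | Power for 0.30 | Difference detectable with 80% power |
|---|---|---|---|---|
| 0.10 | 1 | 0.10 | 79.3% | 0.30 |
| 0.10 | 3 | 0.0333 | 61.9% | 0.36 |
| 0.10 | 4 | 0.025 | 57.2% | 0.37 |
| 0.05 | 1 | 0.05 | 68.5% | 0.34 |
| 0.05 | 3 | 0.0167 | 50.8% | 0.39 |
| 0.05 | 4 | 0.0125 | 46.4% | 0.40 |

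Table 3's 35-point difference, corrected for four tests, has 73.6% power at family alpha 0.10 and 63.6% at 0.05.

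**Does permutation recover the loss?** A max-statistic permutation across genes was simulated (1,500 trials, 1,000 permutations each, independent genes at 20% frequency). Power was 60.6% and 49.9% for three tests, and 55.7% and 44.7% for four, at family alpha 0.10 and 0.05. These are close to the alpha/m values.

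**The permutation rule as worded.** It compares each test with permutations of that same test. This gives an empirical p-value for one gene and leaves the threshold unadjusted for the other genes. Power then stays near the single-gene level (about 75–79% at 0.10). With four independent tests at 0.10, family-wise error is 1 − 0.90⁴ = 34%.

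**Other rows of Table 3 at alpha 0.05, same formula.** 15%: 86.0%; 30%: 80.0%; 40%: 76.5%; 50%: 75.1%. The last two fall short; 80% needs about 0.28 and 0.275 rather than 0.27 and 0.26.

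**The case against.** The best defence is that the power sentence states its own alpha, concerns one gene, and is correct on those terms. That stands. A reader might infer an arithmetic error in the 80%, and there is none. The fault is an undefined alpha and family, and a correction left out of the power calculation.

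Other parts of the defence limit the point:

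- **Number of tests.** A reader might apply the list of at least 24 recurrently mutated genes and conclude that power is far lower still. Section 1.3 places that list under the goal on velocity and depth of clearance, not under mutation against response, so it does not set the primary family.
- **Clinical threshold.** A reader might take 30 points as the plan's own clinical cut-off. The wording is "at least 30% of clinical response could be attributed to the presence of a specific mutation", which reads as a share of responses rather than a difference in rates. At 20% frequency, a 30-point difference accounts for 0.20 × 0.30 / 0.45 = 13% of responses. The documents do not equate the two.
- **Choice of alpha.** Two-sided 0.10 is a legitimate choice for a single-arm phase II biomarker study, and reporting 95% intervals does not fix a test level. The objection is to leaving the level unstated.
- **More favourable settings.** At 30% frequency, 30 points does have 80% power at 0.05. Section 14.2.5 plans a comparison of patients with any of the four genes mutated, and Section 1.1 puts such patients at nearly half. At 45–50% frequency the figure is 86–87% at 0.05, uncorrected. That comparison is listed as an exploratory subgroup and does not support the single-gene claim.
- **More evaluable patients.** If all 125 enrolled patients were evaluable, four-test power would be 69% (family alpha 0.10) or 58% (0.05), still below 80%.

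**Conclusion.** The point holds as a fault of specification and multiplicity. The stated 80% applies only to one gene at unadjusted two-sided 0.10. For the same 30-point difference, power is 68.5% at Table 3's alpha. With family-wise correction over three or four tests it is 57–62% at family alpha 0.10 and 46–51% at 0.05. If the permutation rule is applied literally, power is roughly preserved but the promised correction across genes does not take place. The plan cannot claim both.

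The corrected figures rest on an assumed three or four tests, 20% mutation frequency, 45% overall response, 100 evaluable patients and nearly independent genes. The documents give no number of tests and no family alpha, so a range is the most that can be stated. The shortfall in Table 3's 40% and 50% rows is real but minor. Those rows lie outside the 15–30% single-gene range that the plan itself cites.

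**What to change.** 1. State one alpha for the primary analysis and say that it is family-wise.
2. Define the confirmatory family: either DNMT3A, IDH1/2 and TET2 (three tests) or the four genes separately (four tests). Label all other genes exploratory.
3. Replace the permutation rule with a min-P (max-statistic) permutation across that family.
4. Restate the power sentence and Table 3 at the resulting level. For 20% frequency, N = 100 and 80% power, the detectable difference is about 0.36 (three tests) or 0.37 (four) at family alpha 0.10, and 0.39 or 0.40 at 0.05. If an uncorrected figure is kept for reference, it is about 0.34 at 0.05 and should be labelled as single-gene.
5. In the same recalculation, correct the 40% and 50% rows. At uncorrected 0.05 they should read about 0.28 and 0.275.

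The cost is a change of wording in Section 14.2.2 and one recomputed table, with no extra patients. The drawback is a less favourable stated power. Keeping 80% power for 30 points at 20% frequency would instead need about 150–160 evaluable patients at family alpha 0.10, or 175–190 at 0.05, for three to four tests.

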1.3 Correlative Studies

All correlative studies will be collected under HRPO# 201011766 (“Tissue Acquisition for Analysis of Genetic Progression Factors in Hematologic Diseases”) that all patients will be concurrently enrolled in. The goals of the correlative studies include:

1. To correlate patient-specific mutations with response to decitabine.
We will perform exome sequencing of each patient’s pre-study bone marrow sample and skin sample. We will determine AML/MDS-associated variants found in the bone marrow, but not skin sample. We will correlate the presence of mutations with response (especially mutations in *DNMT3A*, *IDH1*, *IDH2*, and *TET2*). This study is powered to identify mutations with >80% sensitivity to predict decitabine response if used as a clinical assay.
2. To correlate the velocity and depth of response with response to decitabine.
We will assess tumor burden by allele frequency of patient-specific mutations in bone marrow samples collected pre study, Cycle 1 Day 10±1, Cycle 1 Day 28±4, and Cycle 2 Day 28±4. We will assess mutations in at least 24 recurrently mutated genes (including, but not limited to: *FLT3*, *DNMT3A*, *NPM1*, *TET2*, *WT1*, *IDH1*, *IDH2*, *RUNX1*, *NRAS*, *TP53*, *U2AF1*, *KRAS*, *PHF6*, *MSTP9*, *PTPN11*, *KIT*, *SMC3*, *PRUNE2*, *ETV6*, *CEBPA*, *SMC1A*, *ASXL1*, *STAG2*, *RAD21*) as well as all patient-specific mutations discovered during exome sequencing. The leukemic allele frequency will be measured using the Illumina MySeq or HiSeq platform using DNA capture by gene specific biotinylated-oligonucleotides. Patient bone marrow samples will be assessed pre-study, Cycle 1 Day 10 ± 1, Cycle 1 Day 28 ± 4, and Cycle 2 Day 28 ± 4 and compared with patient specific skin samples (normal control). The velocity of response will be calculated as the natural log rate of patient-specific mutation allele frequency clearance. Depth of response will be defined as the lowest patient-specific mutation

allele frequency in a bone marrow sample. The velocity and depth of tumor response will be correlated to:

- Achievement of clinical CR,
- Time to best response,
- Mutational status,
- Time to disease progression.

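### Table 3's sensitivity column is really the response rate among mutation carriers, so the claim of more than 80% sensitivity has no support and is impossible for any single gene at 15–30% frequency

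*Combined protocol and SAP*

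**What the plan says.** Section 14.2.2 (Primary Endpoint Analysis) names the method: "A power analysis was performed using Chi-square test for the association between mutation and response to decitabine". Table 3 takes 100 evaluable patients and lists a detectable difference in response rate for each of five mutation frequencies, "assuming an expected overall 45% CR/CRi rate and 80% power". The differences are 0.40, 0.35, 0.30, 0.27 and 0.26 for frequencies of 15, 20, 30, 40 and 50%. The table title, which begins "Detectable mutation associated response rates (80% power", sets alpha at 0.05, but the worked example in the text says that "100 patients will provide 80% power to detect 30% difference at a 2-sided 0.1 alpha error". The same section expects each named gene (DNMT3A, IDH1/2, TET2) to be mutated in 15–30% of patients.

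The last column is headed "Sensitivity of mutation to predict response at minimum detectable response difference" and reads 80, 75, 67, 61 and 58%.

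Section 1.3 item 1 states: "This study is powered to identify mutations with >80% sensitivity to predict decitabine response if used as a clinical assay". The table and this sentence recur in every protocol version in the file.

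**The concern.** Sensitivity is the proportion of responders who carry the mutation. At a fixed overall response rate it should rise as the mutation becomes more common, unless the effect shrinks very fast. The printed column falls. The 15% row fails a simple count: of 100 patients, 15 carry the mutation and 45 respond, and 80% of 45 is 36, so 15 carriers cannot supply 36 responders.

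This matters because Section 14.2.2 gives the purpose of the study as deciding whether a mutation merits testing before treatment. A reader of Section 1.3 would expect such a test to find at least four responders in five. In the 15% row of Table 3 it would find about one in four.

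**Working it through.** **Inputs** (Section 14.2.2): N = 100; overall response 0.45; mutation frequency f and difference d from Table 3; chi-square test; alpha 0.05. The table title does not state sidedness. I take it as two-sided, as in the text example.

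**Response rates.** With the overall rate held at 45%, carriers respond at p_mut = 0.45 + (1 − f)d and non-carriers at p_wt = 0.45 − f·d.

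**Reproducing the printed column.** For f = 15%, p_mut = 0.45 + 0.85 × 0.40 = 0.79, against 80% printed. All five rows agree within 2 points. As a cross-check, treat the printed column as p_mut, subtract d to get p_wt, and average over carriers and non-carriers. The overall response rates are 46, 47, 46, 44.8 and 45%, close to the assumed 45% in every row. The column is therefore P(response | mutation).

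**True sensitivity.** P(mutation | response) = f·p_mut / 0.45. For f = 15% this is 0.15 × 0.79 / 0.45 = 0.263. The ceiling, reached if every carrier responds, is f / 0.45, or 100% if that is smaller.

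| f | d printed | Printed as sensitivity | p_mut | True sensitivity | Ceiling |
|---|---|---|---|---|---|
| 15% | 0.40 | 80% | 79.0% | 26% | 33% |
| 20% | 0.35 | 75% | 73.0% | 32% | 44% |
| 30% | 0.30 | 67% | 66.0% | 44% | 67% |
| 40% | 0.27 | 61% | 61.2% | 54% | 89% |
| 50% | 0.26 | 58% | 58.0% | 64% | 100% |

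**When 80% is reachable.** Sensitivity of 0.80 needs f·p_mut = 0.80 × 0.45 = 0.36. Since p_mut cannot exceed 1, f must be at least 36%. At f = 50%, p_mut = 0.36 / 0.50 = 0.72 and p_wt = (0.45 − 0.36) / 0.50 = 0.18, a difference of 0.54. Power for that difference exceeds 99%.

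**Power at the printed differences.** Pooled-variance formula: power = Φ[(d − z·s0) / s1], with z = 1.96 at two-sided 0.05, s0² = 0.45 × 0.55 × (1/n_mut + 1/n_wt) and s1² = p_mut(1 − p_mut)/n_mut + p_wt(1 − p_wt)/n_wt. With z for two-sided alpha 0.10, the plan's text example (f = 20%, d = 0.30) gives 79.3%, so the formula reproduces it. At two-sided 0.05 that example would have 68.5%.

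- 15% row: s0 = 0.1393, s1 = 0.1177, and (0.40 − 0.2731) / 0.1177 = 1.078, giving 86.0%.
- 50% row: s0 = 0.0995, s1 = 0.0960, and (0.26 − 0.1950) / 0.0960 = 0.677, giving 75.1%.

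| f | Pooled chi-square | Exact Pearson | Noncentral chi-square | d for 80% (pooled) |
|---|---|---|---|---|
| 15% | 86.0% | 86.2% | 81.9% | 0.375 |
| 20% | 82.6% | 82.8% | 80.3% | 0.340 |
| 30% | 80.0% | 80.3% | 78.9% | 0.300 |
| 40% | 76.5% | 77.5% | 75.8% | 0.282 |
| 50% | 75.1% | 76.8% | 74.3% | 0.275 |

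The unpooled formula gives 78.3% and 77.3% in the last two rows. Continuity-corrected and Fisher versions are lower there (68–72%).

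**The case against.** The strongest reply on sensitivity is that Section 1.3 speaks of mutations in general, and Section 14.2.2 foresees combining characteristics into larger groups. Section 1.1 says that about half of patients carry a mutation in one of the four genes, and for a marker that common 80% sensitivity is attainable. This stands. A reader might infer that the claim can never be met, and the documents do not support that. They exclude it only for markers carried by fewer than 36% of patients. The reply does not rescue the sentence, because no row of Table 3 exceeds 64%, and at 50% frequency a difference about twice the printed one is needed.

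It could also be said that if a mutation marks resistance, its absence could be a sensitive predictor of response. That is true, but neither the column heading nor the sentence describes it.

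On power, the plan names a chi-square test but no formula. The noncentral version gives 80%-power differences of 0.390, 0.348, 0.304, 0.285 and 0.279, all within 0.02 of the printed values, so the size of any mismatch depends on the formula. A reader might also infer that the primary analysis is underpowered. At 15–30%, the range expected for the named genes, the table is about right or conservative. The any-of-four-genes contrast, to which the 50% row would apply, appears only as an exploratory subgroup in Section 14.2.5, with no power claimed for it.

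**Conclusion.** The column label is wrong as written, and the sentence in Section 1.3 states a design property that Table 3 does not have. At the printed differences, sensitivity is 26–64%, against 58–80% printed. For a single gene at 15–30% frequency it cannot exceed 33–67%. This conclusion needs no power formula. It rests on the plan's 45% response rate and on carriers being the predicted responders. The ceiling scales with the response rate: a gene at 30% frequency could reach 80% sensitivity only if overall response were at most 0.30 / 0.80 = 37.5% and every carrier responded.

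The power point is secondary. The 15–30% rows give 80–86% (pooled) or 79–82% (noncentral). The 40% and 50% rows give about 74–78% by the uncorrected formulas, a shortfall of about 0.01–0.02 in the detectable difference. This assumes two-sided alpha 0.05, overall response held at 45% and carriers responding more often.

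**What to change.** 1. Rename the last column of Table 3 *Response rate among carriers (positive predictive value)*, and add a column of true sensitivity.
2. Withdraw the sentence in Section 1.3 item 1, or restate it as a response rate among carriers at a stated mutation frequency.
3. Choose one alpha for the table and the worked example, name the formula, and recompute. With pooled chi-square at two-sided 0.05 the differences are about 0.375, 0.340, 0.300, 0.282 and 0.275. They should be rounded up so that each row delivers 80%; rounding down to 0.37 and 0.27 in the first and last rows gives 78.7% and 78.3%. If two-sided 0.10 is intended, the pooled values are 0.335, 0.303, 0.267, 0.250 and 0.245.

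The cost is a correction to one table and one sentence. The 40% and 50% rows become slightly less favourable at alpha 0.05. The planned tests, the sample size and the study procedures are unaffected.

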14.2.3 Secondary Endpoint Analyses

The overall response rate (CR/CRi/PR) and complete response rate (CR/CRi) will be compared with historical controls[2], and the 95% confidence intervals will be provided.

The rate of patient specific mutation clearance after 10, 28, and 56 days of therapy will be determined using an Illumina based platform. We will compare the rate of mutation clearance between the patients who achieve a CR/CRi after 4 cycles and those who do not. We anticipate that we will identify between 6 and 25 exonic SNVs per case (the range obtained with >200 AML samples sequenced to date with whole genome or exome sequencing), and that the expected 95% confidence interval of the mean variant allele frequency will be $\pm 2.56\%$ and $\pm 1.25\%$,

respectively, if we assume an anticipated standard deviation of 3.2% within the same clone. The change of tumor burden over time and its association with clinical response will be assessed using 2-way ANOVA for repeated measurement data, followed by the ad-hoc multiple comparisons for between-group differences (e.g., responders vs. non-responders) at given time points as well as the between-time differences within each group. The resultant critical P values will also be corrected using permutation analysis for multiple testing.

The percent decrease in bone marrow methylcytosine will be calculated on day 10 ± 1 . We will compare this reduction with previously published data and between the patients who achieve CR/CRi and those who do not. The correlation of peak plasma levels of decitabine with response will be assessed using 2-sample t-test or Mann-Whitney non-parametric rank-sum test as appropriate. The change of total bone marrow DNA methylcytosine from baseline and its association with both steady-state plasma drug levels and response will be assessed using 2-way ANOVA for repeated measurement data, followed by the ad-hoc multiple comparisons for between-group differences (e.g., responders vs. non-responders) and between-time differences. Similar analyses will be performed for the correlation of expression profiles and SNP analysis with pharmacokinetic data.

Statistical power justification. A power analysis was performed using two-sample t-test for between-group difference and paired t-test for the change over time. For tumor clearance, this will provide $> 99\%$ power to detect a 10% difference in the means at two separate time points for clones with 6 or more variants, and $> 98\%$ power to detect a 15% difference if there are 3 or more variants per clone with $\alpha = 0.05$ (power will decrease to 91% and 82%, respectively, in cases where the standard deviation is 4.7%, the maximum we have observed thus far). For pharmacologic correlations, we anticipate 85% power to determine a 25 ng/ml difference between the average C_{\max} of 45 evaluable responders and 55 evaluable non-responders with an anticipated average C_{\max} of 70 ng/ml and a standard deviation of 40 ng/ml within the entire cohort, and with $\alpha = 0.05$. [22] We believe a less significant difference would not be sufficient to warrant application in clinical decision making (i.e. whether to continue therapy for more than 1 cycle). We anticipate 99% power to determine a difference of 20% in the reduction of bone marrow methylcytosine between 45 evaluable responders and 55 evaluable non-responders with an expected standard deviation of 15% and $\alpha = 0.05$. [28, 66-68] The difference in methylcytosine reduction previously observed was 30% between patients achieving CR/PR and those with only hematologic improvement. [28]

Time to relapse and time to death will also be listed for each patient.

